5. TABLE OF EVENTS

Table 1: Table of Events

	Study Procedures	Screening	Initiation of Dose Escalation	Treatment				Early Termination (ET)
			Day 1 ^{a,b}	Day 8	Week 4 ^b	Week 8 ^b	Week 12 ^b	
		Day -35 to 0	Day 1 (Baseline)	Day 8	Day 28 ±3 ^{aa}	Day 56 ±3 ^{aa}	Day 84 ±3 ^{aa}	Day ET

Table 1: Table of Events (Continued)

	Study Procedures	Screening	Initiation of Dose Escalation	Treatment				Early Termination (ET)
			Day 1 ^{a,b}	Day 8	Week 4 ^b	Week 8 ^b	Week 12 ^b	
		Day -35 to 0	Day 1 (Baseline)	Day 8	Day 28 ±3 ^{aa}	Day 56 ±3 ^{aa}	Day 84 ±3 ^{aa}	Day ET

Table 1: Table of Events (Continued)

[figure not shown]
	Study Procedures	Screening	Initiation of Dose Escalation	Treatment				Early Termination (ET)		
			Day 1 ^{a,b}	Day 8	Week 4 ^b	Week 8 ^b	Week 12 ^b			
		Day -35 to 0	Day 1 (Baseline)	Day 8	Day 28 ±3 ^{aa}	Day 56 ±3 ^{aa}	Day 84 ±3 ^{aa}	Day ET		
Efficacy Assessments	Electronic diary ^w	X	X		X	X	X	X		
	CDAI	X ^q	X		X	X	X ^r	X		
	Colonoscopy/SES-CD/ CDEIS/colonic biopsy ^s	X					X	X		

[figure not shown]
Abbreviations:

CDAI = Crohn's Disease Activity Index; CDEIS = Crohn's Disease Endoscopic Index of Severity;
 ET = early termination;

[figure not shown]
^a [Redacted text]

^b Study visits should be scheduled in the morning, where possible, and on study visit days, subjects should be instructed to withhold the dose until the study visit and the dose should be administered during the visit after the PK draw.

[figure not shown]

^s Colonoscopy should be performed upon confirmation of eligibility based on CDAI at Screening and other entry criteria, if possible. A subject's colonoscopy from a previous screening in this study may be used if within 35 days of randomization. If early termination visit is less than 4 weeks after Baseline, no further colonoscopy is required. At Week 12, a colonoscopy should be performed either on day of visit or no more than 7 days prior to the visit date. Intestinal mucosal biopsies will be performed when the ileocolonoscopies are done as indicated in [Table 1](#), except in countries or sites with local restrictions.

^w The electronic daily diary will be provided to subjects at the Screening Visit. Subject compliance with the completion of the diary data should be assessed at each study visit.

6. PROCEDURES

6.1. Screening Period

Written, signed, and dated informed consent from the subject prior to the performance of any study-related procedures must be obtained by the Investigator or designee (refer to Section 16.3 for further details regarding obtaining subject's informed consent).

Screening procedures must be completed within 35 days prior to receiving the first dose of IP. All screening assessments and procedures as per Table 1 are to be performed by the Investigator or a qualified designee. During the screening period,

See Appendix C for further SARS-CoV-2 guidance.

A screen failure is defined as a subject who has given informed consent and failed to meet the inclusion and/or exclusion criteria. Subjects who fail to meet the inclusion/exclusion criteria can be rescreened per Investigator discretion. Additional screening attempts beyond the first should be approved by the Medical Monitor prior to rescreening.

[figure not shown]
During Screening, the subject's prior use of medications to treat CD and whether he/she responded to adequate treatment with each medication will be assessed and documented.

[figure not shown]
It will also be documented when the subject has been intolerant to 1 of these therapies (eg, unable to achieve doses as indicated in [Appendix B](#), dose levels, or treatment durations because of treatment-related side effects and/or laboratory abnormalities).

Screening period schedule and procedures are provided in the Table of Events ([Table 1](#)). Each subject must be re-consented prior to each screening attempt. A subject's colonoscopy from a previous screening in this study may be used if within 35 days of randomization.

6.2. Treatment Period

Eligible subjects will be randomized to treatment on Day 1. Visits, assessments, and procedures will be performed as per the Table of Events in [Table 1](#).

[figure not shown]

6.2.4. Study Stopping Rules

The Sponsor has the right to terminate the study for safety reasons. In addition, the Sponsor may terminate the study for administrative reasons. In all cases, all necessary measures must be taken to guarantee appropriate safety follow-up of all subjects already included in the study.

The Institutional Review Board (IRB) or Independent Ethics Committee (IEC) and the Regulatory Authorities will be informed in writing about any termination of the study.

6.3.

6.3.2. Efficacy Assessments

[figure not shown]
See Section 2 for a description of study endpoints.

6.3.2.1. Primary Efficacy Assessment

The CDAI will be used to evaluate the primary efficacy endpoint.

6.3.2.1.1. Crohn's Disease Activity Index

The CDAI is a composite score that is used to measure the clinical activity of CD. The CDAI uses a questionnaire with responses scored numerically and weighted. Scores range from 0 to approximately 600, with higher scores indicating greater disease activity. The 8 components used to assess the CDAI and their weighting factors are noted in [Table 3](#). The definitions of mild, moderate, and severe CD are provided in [Table 4](#).

Subject-reported components of the CDAI (stool frequency and abdominal pain components and general well-being) will be collected in an electronic diary. Subjects will complete their electronic diary starting at screening visit and will continue throughout the study.

Subjects will be instructed on the use and completion of questions on the electronic diary.

The diary entries will be reviewed by site personnel during Screening and throughout the study.

Table 3: Crohn's Disease Activity Index Assessment

Clinical or Laboratory Variable	Weighting Factor, ×
Number of liquid or soft stools each day for 7 days	2
Abdominal pain (graded from 0-3 on severity) each day for 7 days	5
General well-being, assessed from 0 (well) to 4 (terrible) daily for 7 days	7
Presence of complications ^b	20
Taking diphenoxylate/atropine, loperamide, or opiates for diarrhea	30
Presence of an abdominal mass (0 as none, 2 as questionable, 5 as definite)	10
Hematocrit (47-HCT in men and 42-HCT in women)	6
Percentage deviation from standard weight	1
Total Score^b	

Abbreviations: HCT = hematocrit.

^b One point each is added for each set of complications: arthritis or arthralgia; iritis or uveitis; erythema nodosum, pyoderma gangrenosum, aphthous stomatitis; anal fissure, fistula or perirectal abscess; other bowel-related fistula; febrile (fever) episode over 100 degrees during the past week.

Table 4: Crohn's Disease Severity Definitions

Severity	CDAI Score
Mild	150-219
Moderate	220-450
Severe	> 450

Abbreviations: CDAI = Crohn's Disease Activity Index.

6.3.2.1.2. Abdominal Pain and Stool Frequency

The abdominal pain and stool frequency scores are based on 2 components of the CDAI ([Khanna 2015](#)). See Section 6.3.2.1 above for more details.

Stool frequency and abdominal pain, as described in Section 6.3.2.1, will be obtained and calculated without a weighting factor for use as part of the inclusion criteria. These un-weighted subject-reported assessments will also be used as efficacy endpoints (Section 2).

[REDACTED] is an additional tool for the visual evaluation of diarrhea, and will be collected from all subjects in the electronic diary.

6.3.2.2. Simple Endoscopic Score for Crohn's Disease

The SES-CD assesses the degree of inflammation. The SES-CD assesses the following four components: size of ulcers, ulcerated surface, affected surface, and presence of narrowing. Each of these components are scored on a scale of 0 to 3 as outlined in [Table 5](#).

In the SES-CD, each of these 4 components are assessed in the 5 segments of the ileum and colon: ileum, right, transverse, left (descending and sigmoid), and rectum. The SES-CD is the sum of the individual scores of each of the components across the 5 segments.

Endoscopic response has not yet been validated and may be defined as a 25% to 50% or greater decrease in SES-CD from baseline. [REDACTED]

[REDACTED], the same endoscopist and the same diameter colonoscope as used in screening should be used throughout the study wherever possible.

[REDACTED] Details regarding the biopsies are provided in the biopsy manual and Histology Image Charter. Colonoscopies will be read at a centralized reading facility in a process outlined in the Endoscopy Image Charter. Centralized reading will be the primary assessment for endoscopy; local endoscopy scores will also be collected.

Local colonoscopy may be used for baseline assessments in the Induction Study if within 35 days of baseline, consent was obtained from the subject for use in a clinical study, and video quality and format is considered adequate for evaluation by centralized reading facility.

Table 5: Definitions of Simple Endoscopic Score for Crohn's Disease (SES-CD)

Variable	SES-CD Values			
	0	1	2	3
Size of ulcers	None	Aphthous ulcers (0.1 to 0.5 cm)	Large ulcers (0.5 to 2 cm)	Very large ulcers (>2 cm)
Ulcerated surface	None	< 10%	10%-30%	>30%
Affected surface	Unaffected segment	< 50%	50%-75%	>75%
Presence of narrowings	None	Single, can be passed	Multiple, can be passed	Cannot be passed

6.3.2.3. Histology

A central reader will evaluate biopsies taken during colonoscopy and determine the Global Histologic Disease Activity Score (GHAS) (Table 6) [REDACTED]

[REDACTED]. Biopsies will be taken from the explored ileal and colonic segments. The GHAS [REDACTED] scores provided [REDACTED] will be used for histopathology endpoints.

Table 6: GHAS Grading System

[figure not shown]
GHAS Descriptors and Levels	
Epithelial damage	0: Normal 1: Focal Pathology 2: Extensive Pathology
Architectural changes	0: Normal 1: Moderately disturbed (< 50%) 2: Severely disturbed (> 50%)
Infiltration of mononuclear cells in the lamina propria	0: Normal 1: Moderate increase 2: Severe increase
Infiltration of polymorphonuclear cells in the lamina propria	0: Normal 1: Moderate increase 2: Severe increase
Polymorphonuclear cells in epithelium	0: Absent 1: In surface epithelium 2: Cryptitis 3: Crypt abscess
Presence of erosion and/or ulcers	0: No 1: Yes

Table 6: GHAS Grading System (Continued)

GHAS Descriptors and Levels	
Presence of granuloma	0: No 1: Yes
Number of biopsy specimens affected ^a	0: None 1: ≤ 33% 2: > 33%-66% 3: > 66%

Abbreviations: GHAS = Global Histologic Activity Score

^a For individual segments with only one biopsy segment available, determine if the sample is entirely involved or not. If the fragment is not involved, score as '0 – None'. If ≤ 33% of the fragment is involved, score as '1 - ≤ 33%'. If 34 to 66% of the fragment is involved, score as '2 - 34%-66%'. If > 66% of the fragment is involved, score as '3 - > 66%'.

6.3.3. Other Assessments

6.3.3.1. Physical Examination

A complete physical examination will be performed to evaluate the heart, lungs, head and neck, abdomen, skin, extremities, weight, as well as to check for visual symptoms (eg, blurred vision or decreased visual acuity as reported by the patient). Height should be measured and recorded at

screening. A full examination of the skin should be repeated every 6 months. An interim physical examination will include weight, a check for visual symptoms, and an evaluation of body systems with previously noted abnormalities and/or those body systems associated with any new complaints from the patient. See [Table 1](#) for additional details and assessment time points.

6.3.3.2. Vital Signs

Systolic and diastolic blood pressure and pulse will be assessed in a supine and standing position at every visit. An automated validated device may be used, if available. In case the cuff sizes available are not large enough for the patient's arm circumference, a sphygmomanometer with an appropriately sized cuff may be used. Subjects will be carefully monitored after the first dose of investigational drug with a 6 hour post-dose monitoring period of hourly recording of pulse and blood pressure as described in [REDACTED].

6.3.3.3. Electrocardiogram

The 12-lead digital ECG devices will be provided to each clinical site by the central ECG laboratory for the duration of the study. Detailed instructions describing the process for recording and transmission of the digital ECGs will be outlined in the study-specific manual and provided to the site before the start of the study. Paper versions of ECG tracings will be printed and photocopied to preserve the ink if necessary and kept at the site as source documentation. An ECG will be performed while resting. Electrocardiograms will be performed before the first dose of IP in all subjects and 2, 4 and 6 hours after the first dose of investigational drug administration for at-risk subjects (as outlined [REDACTED]), or in all subjects if deemed necessary by national and local requirements, on Day 1 while the subject is in the clinic.

All ECGs will be evaluated by the treating physician, with input from a local cardiologist (upon approval from a Medical Monitor) or a central reader to confirm if additional monitoring is required. If a local cardiologist is not available upon discharge, discharge criteria were evaluated by the treating physician, and the central results are assessed as abnormal or unmeasurable then the subject will need to return for further evaluation.

[REDACTED]

[figure not shown]
Only clinically significant abnormalities should be reported in the medical history/current medical conditions or the AE eCRF.

[figure not shown]
6.3.3.4. Pulmonary Function Test

[figure not shown]
The pulmonary function test (PFT) refers to "pulmonary function test – no bronchodilator" (eg, spirometry which includes total and timed vital capacity, and expiratory flow rate measurement). [REDACTED]

Pulmonary function tests may be performed at a qualified pulmonary function laboratory, respiratory department, or at the clinical trial site. If being performed at the clinical trial site, the Principal Investigator may delegate the performance of this test to any staff member that is qualified to perform the pulmonary function test. If the pulmonary function test results are not within normal range and are considered clinically significant, the results must be verified by a pulmonologist, and potential confounding factors identified. Please refer to the American

Thoracic Society / European Respiratory Society guidelines for standardization of spirometry and single breath determination of carbon monoxide uptake in the lung ([MacIntyre 2005](#); [Miller 2005a](#); [Miller 2005b](#)).

7. DESCRIPTION OF STUDY TREATMENTS

7.1. Description of Investigational Product

Ozanimod capsules will be manufactured, quality control tested, and released in accordance with Good Manufacturing Practices (GMP).

Ozanimod and matching placebo will be provided as powder-filled capsules. Ozanimod drug substance is blended with microcrystalline cellulose, colloidal silicon dioxide, croscarmellose sodium and magnesium stearate in opaque hard-gelatin capsules. Two ozanimod dosage strengths have been prepared for the clinical investigations: 0.23 mg (size 4 capsule; equivalent to 0.25 mg ozanimod HCl) and 0.92 mg (size 4 capsule; equivalent to 1 mg ozanimod HCl). For matching placebo, the same size 4 opaque hard-gelatin capsules will contain the same blended excipients described above. Both doses of ozanimod and placebo capsules are identical in appearance.

The capsules will be orally administered singularly, or in varying combinations, to achieve the desired dose for clinical studies.

There is no provision for dose adjustments in this study. Subjects who cannot tolerate IP must be withdrawn from the study.

7.2. Treatment Administration and Schedule

Following the 7-day dose escalation, subjects will receive a single 0.92 mg oral dose of ozanimod (equivalent to ozanimod HCl 1 mg) or matching placebo administered daily. The dose escalation regime is as follows:

- Day 1 through 4: Ozanimod 0.23 mg (equivalent to ozanimod HCl 0.25 mg) (or matched placebo)
- Day 5 through 7: Ozanimod 0.46 mg daily (equivalent to ozanimod HCl 0.5 mg) (administered as two 0.23-mg capsules or 2 matched placebo capsules)
- Day 8 through Week 12: Ozanimod 0.92 mg daily (equivalent to ozanimod HCl 1 mg) (or matched placebo)

[REDACTED]

If subjects miss dosing for more than 14 days, they are required to complete the 7-day dose escalation regimen as outlined above, including [REDACTED].

An overdose is any dose of IP given to a subject or taken by a subject that exceeds the dose described in the protocol. Any overdose, with or without associated AEs, must be promptly reported to the Medical Monitor or other designated Drug Safety Center. The overdose should be recorded in the study exposure eCRF. AEs associated with an overdose should be reported on relevant AE/SAE sections in the eCRF.

Please refer to the Investigator's Brochure for more information.

7.2.1. Instructions for Missed Doses

Subjects should be instructed that if they forget to take a dose, they can take the dose within 4 hours of the normal dosing time. If the subject vomits the capsule, he/she should be instructed not to take another capsule on the same day, but to take the next dose at the regular time on the following day.

If a single dose is missed during the first 2 weeks of treatment, or for more than 7 consecutive days during Days 15 to 28, treatment must be reinitiated using the [REDACTED]

[REDACTED] If a subject misses a dose during dose escalation, the Medical Monitor should be contacted to discuss completing the dose escalation schedule. The missed dose and extended days for escalation need to be documented as appropriate in the eCRFs.

If a subject misses more than 14 consecutive doses for any reason, the Medical Monitor must be contacted to discuss procedures for resuming therapy, [REDACTED]

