10.2.5. Action Taken

Prior to interruption, the Investigator may contact the Medical Monitor and forward appropriate supporting documents for review and discussion.

The Investigator will report the action taken with IP as a result of an AE or SAE, as applicable (eg, discontinuation, interruption, or dose reduction of IP, as appropriate) and report if concomitant and/or additional treatments were given for the event.

If dosing is interrupted, the Investigator should contact the Medical Monitor to discuss treatment reinitiation (Section 7.2.1). See Section 14 for permanent discontinuation of IP.

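### Do the two missed-dose rules in protocol Section 7.2.1 conflict for a dose missed during the Day 1-7 escalation?

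*Combined protocol and SAP*

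**What the plan says.** Section 7.2 sets a 7-day escalation: one step on Days 1-4, a second on Days 5-7 ("Day 5 through 7: Ozanimod 0.46 mg daily"), and full dose from Day 8 to Week 12. Placebo follows a matching schedule.

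Section 7.2.1 then gives these missed-dose instructions:

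- **Early missed dose.** The trigger is "If a single dose is missed during the first 2 weeks of treatment", with a second limb for longer gaps in Days 15-28. The action is "treatment must be reinitiated using the", after which the text is redacted.
- **Missed dose in escalation.** After the redaction comes "If a subject misses a dose during dose escalation, the Medical Monitor should be contacted to discuss completing the dose escalation schedule". The next sentence adds "The missed dose and extended days for escalation need to be documented as appropriate in the eCRFs".
- **Long gap.** "If a subject misses more than 14 consecutive doses for any reason, the Medical Monitor must be contacted to discuss procedures for resuming therapy", again followed by redacted text.

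Two other places bear on this. Section 7.2 says "If subjects miss dosing for more than 14 days, they are required to complete the 7-day dose escalation regimen" and then runs into a redaction. Section 10.2.5 tells the investigator, when dosing is interrupted, to speak to the Medical Monitor about reinitiation, and cites Section 7.2.1.

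**The concern.** The first two rules in Section 7.2.1 share cases, and neither visible trigger excludes the other's. For one missed capsule in the first week, a site reads that treatment *must* be reinitiated and also that the Medical Monitor *should* be called about completing the schedule, with extra escalation days recorded. Taken quickly, the first means start again and the second means carry on, and the verbs carry different force.

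This falls in the first week of a drug whose first dose is followed by 6 hours of hourly pulse and blood pressure recording (Section 6.3.3.2). If sites read the rules differently, subjects with the same missed dose could reach full dose on different days. It might then be disputed whether a given handling was a deviation relevant to the per-protocol population.

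There is a lesser worry about long gaps: Section 7.2 counts days, Section 7.2.1 counts consecutive doses, and Section 10.2.5 uses weaker language than either.

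**Working it through.** No sample size, power or type I error figure is involved, and the plan states no figure to reproduce. The check compares day ranges and texts.

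**1. Overlap of triggers.** Escalation is Days 1-7 (Section 7.2). The early-dose rule covers the first 2 weeks, Days 1-14, since its second limb starts at Day 15 (Section 7.2.1).

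| Day of missed dose | Reinitiation rule | Escalation rule |
|---|---|---|
| 1-7 | applies | applies |
| 8-14 | applies | does not apply |

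The overlap is complete: 7 of 7 escalation days.

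**2. Do the actions conflict?** Overlapping triggers conflict only if the actions cannot both be carried out.

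- The early-dose rule requires reinitiation; the escalation rule advises a call about completing the schedule. A site can do both.
- Completing need not mean continuing. In Section 7.2 the same verb describes going through the whole 7-day regimen again after a long gap: "If subjects miss dosing for more than 14 days, they are required to complete the 7-day dose escalation regimen".
- Extra escalation days are recorded after a restart as well as after an extension, so "The missed dose and extended days for escalation need to be documented as appropriate in the eCRFs" fits either.
- Section 10.2.5 already joins Medical Monitor contact with reinitiation.

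**3. Do they differ in force?** The mandatory verb governs reinitiation; the advisory verb governs the call. These are different acts, and a required act with an advised consultation is coherent.

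**4. Long gaps.** Dosing is once daily, so more than 14 consecutive doses is more than 14 days without dosing. The two counts describe the same interval. Section 10.2.5 covers any interruption and Section 7.2.1 only the long ones, so firmer wording for the longer gap is consistent.

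**5. Size under the divergent reading.** Two assumptions are needed, and the documents state neither: the redacted regimen is the full 7 days begun the day after the missed dose, and completing means a one-day extension. For a dose missed on Day d:

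- restart: first full dose on Day (d + 1) + 7 = d + 8
- extension: first full dose on Day 8 + 1 = 9
- difference: (d + 8) - 9 = d - 1

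For d = 1 to 7 this gives 0, 1, 2, 3, 4, 5 and 6 days. The sum is 21 and the mean 21/7 = 3 days, or 3/84 = 3.6% of the 12 weeks; the largest is 6/84 = 7.1%. Day 1 is the in-clinic first dose, so a missed Day 1 is hardly a case; without it the mean is 21/6 = 3.5 days. A shorter redacted regimen gives smaller differences. Under the cumulative reading the difference is 0.

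**6. Reach into the analysis.** The primary analysis uses the ITT population by randomized arm with non-responder imputation (Sections 9.2 and 9.6.2). A missed dose is not among the treatment failure rules (Section 9.8). One missed dose in 84 days is 1/84 = 1.2%, far from the 80% compliance limit in Section 7.6. The instructions are the same for both arms under blinding.

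**The case for a change.** The strongest case for acting is that the concern rests on sentences that are present, not on missing text. Both triggers, both verbs and both actions can be read. Restarting and completing are different things in ordinary use, extended days sounds more like carrying on, and nothing visible says to do both or which rule comes first. If both were meant, one clause would say so. The setting is the first week of dosing, and the call that would limit variation between sites is itself only advised.

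Part of this stands. The overlap is real and complete, and the visible text does not say whether the rules are cumulative or alternative. The rest does not hold. The first rule breaks off before its object, and redacted text stands immediately before the second, so an exception or a link may already be there. Redacted text cannot be counted as absent. Whether first-dose monitoring is repeated on reinitiation is likewise not visible. The visible wording does not prove the cumulative reading, but it allows it, and that is enough to say that a contradiction has not been shown.

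**Conclusion.** The concern does not call for a change. The two rules in Section 7.2.1 share all 7 escalation days, but no conflict in action or force is shown. A site following the visible text would reinitiate and speak to the Medical Monitor. The long-gap wording differs in style only.

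The 0 to 6 day figure is not an estimate of anything the plan specifies. It assumes both the content of the redacted regimen and the disputed meaning of completing, and it is 0 if the rules are cumulative. The number of subjects affected cannot be derived from the documents. No effect on the primary result, the per-protocol set or safety has been demonstrated.

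This conclusion rests on reading the redacted text as possibly settling the relation between the two sentences. Someone with the full protocol can confirm that by reading it. If the relation were unstated there too, the two sentences would need reconciling as a point of wording, with the clinical content left to the sponsor's clinical and safety team. No view is taken here on which dosing rule is right.
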